5.3.1 Intra-patient dose escalations

No intra-patient dose escalation is allowed.

5.3.2 Expansion of dose level(s)

If one out of three patients experience a DLT (as defined in Section 3.1.1, up to six patients will be treated at that dose. If one out of up to six patients experience a DLT, dose escalation will continue. If two out of up to six (i.e. between two and six) patients experience a DLT dose escalation will stop and this dose will be defined as the maximum administered dose (MAD). At least three more patients will be treated at a dose below the MAD to define the MTD.

The MAD could also equal the MTD in the event that dose escalation is stopped before two DLTs are observed at a given dose level, due to the expectation that higher dose levels would be too toxic to administer to patients.

5.4 Dose modifications

5.4.1 Dose interruptions

In the event of drug related toxicity, drug administration must be withheld (except for skin, fatigue, nausea, myalgia or arthralgia, unless these specific toxicities do not respond to supportive measures) until Grade 1 or below or until the patient meets the eligibility criteria parameters.

- On observation of a Grade 2 cardiac toxicity (any causality), both vandetanib and selumetinib should be stopped until resolution.
- On observation of G3 diarrhoea, if this does not resolve within 48 hours, both vandetanib and selumetinib should be stopped until resolution (i.e. until Grade 0 or 1 or until the patient meets the eligibility criteria parameters).
- On observation of non-specific respiratory signs and symptoms, where infectious, neoplastic, and other causes are unlikely or have been excluded and a diagnosis of interstitial lung disease (ILD) is likely or confirmed, both IMPs should be interrupted.

Patients must meet eligibility criteria parameters prior to each cycle and following a treatment interruption if the intention is to re-treat.

The maximum unscheduled dose interruption period is two weeks. Patients failing to recover to NCI CTCAE Grade 1 or less after two weeks will be withdrawn from the study.

There are overlapping toxicities associated with both vandetanib and selumetinib. Therefore it may not be clear which agent is responsible for any observed toxicity. If this is the case then administration of both drugs must be stopped at the same time until resolution to the above criteria.

Vandetanib administration should not be interrupted if possible; the aim is to maintain vandetanib to reduce the requirement to repeat the 'loading' phase of vandetanib administration. Therefore on observation of a Grade 2 drug related toxicity, selumetinib alone can be stopped (vandetanib can continue as a single agent administration). The patient should be closely monitored (whilst on vandetanib alone) to ensure the toxicity resolves to Grade 1 or less within 24 hours. If toxicity continues at same grade or increases within 24 hours then vandetanib should also be stopped.

To note: selumetinib should not be given as a single agent.

5.4.1.1 Management of vandetanib and selumetinib toxicity

Vandetanib and selumetinib have overlapping toxicity profiles. As this is the first time they have been used in combination, there is the risk that the frequency and severity of common toxicities could increase.

5.1.1.1.1 Gastrointestinal toxicities

Initially, no prophylactic anti emetics or anti diarrhoeals will be prescribed however there will be ongoing review of emerging toxicity data throughout the study. If the data shows unacceptable GI toxicity then a change on policy will be implemented for the prescription of prophylactic medications.

On observation of gastrointestinal toxicities, these are to be managed as per hospital guidelines.

5.1.1.1.2 Ocular toxicities

If any grade of toxicity affecting the macula and/or affecting patient's vision is observed then study treatment must be stopped and intensified monitoring should be implemented as per site ophthalmologist recommendation. Restarting treatment will be considered on discussion with the PI, ophthalmologist and Sponsor.

If Grade 1 ocular toxicity is observed which does not affect the macula or patient's vision, then continue study treatment and intensify monitoring as per site ophthalmologist recommendation.

If Grade 2 or above ocular toxicity is observed, not affecting the macula or patient's vision, treatment must be stopped and intensified monitoring should be implemented as per site ophthalmologist recommendation. Restarting treatment will be considered on discussion with the PI, ophthalmologist and Sponsor.

5.1.1.1.3 Guidelines for management of other toxicities

Guidelines for the management of other toxicity observed during the study can be found in the following appendices:

- Skin toxicity (Appendix 5)
- QTc prolongation (Appendix 6). Please also see Appendix 8 for medications known to prolong QTc.

Electrolyte supplementation with regular laboratory monitoring should be used, when appropriate, to maintain electrolytes within normal limits and to prevent an increased risk of QTc prolongation.

Please also see Appendix 8 for medications with high risk of causing Torsade de Pointes (TdP). This appendix also notes guidance for wash out periods and guidelines for acceptable concomitant medications that may be associated with TdP.

- LVEF drop (Appendix 7). This appendix describes suggested investigation and management of asymptomatic decreases in LVEF).
- Hypertension Should be managed according to local trust policy.

Anticipated vandetanib and selumetinib toxicity

Please see the current versions of the vandetanib and selumetinib IBs and the vandetanib and selumetinib IB supplement for anticipated toxicities and toxicities that have been observed in previous clinical trials.

5.4.2 Dose reductions

This section is applicable to both the dose escalation phase and also the expansion cohort.

The dose of the combination treatment will be reduced to the previous dose level for any patient who experiences a DLT. If a patient has a dose reduction, their dose should not be re-escalated. NCI CTCAE Version 4.02 is applicable for Section 5.4.2.

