3.2.1 Dose escalation

The final number of patients recruited to this phase will depend on the number of dose escalations required to reach the RP2D.

In the dose escalation stage of the study, the Sponsor reserves the right to investigate alternative doses of vandetanib and selumetinib in response to emerging safety data. Recruitment into cohorts will follow a “rolling-six” design. Dose assignment for each cohort will be carried out, using all available data, by the Sponsor in conjunction with the CI and PI(s). Cohorts of three to six patients will be entered at each dose level.

If one out of three patients experience a DLT (as defined in Section 3.1.1, up to six patients will be treated at that dose).

If one out of up to six patients experience a DLT, dose escalation will continue.

If two out of up to six (i.e. between two and six) patients experience a DLT dose escalation will stop and this dose will be defined as the maximum administered dose (MAD). At least three more patients will be treated at a dose below the MAD to define the MTD.

Each of the cohorts will assess vandetanib in combination with selumetinib. Selumetinib will initially be administered at three dose levels, 25, 50 and 75 mg (oral, twice daily).

The first three cohorts will initially investigate combining vandetanib (100mg, once daily) with increasing doses of selumetinib as follows:

Study cohort	Vandetanib	Selumetinib
Cohort 1	100 mg po od	25 mg po bd
Cohort 2	100 mg po od	50 mg po bd
Cohort 3	100 mg po od	75 mg po bd

Should MTD not be achieved on completion of Cohort 3, recruitment will continue into additional cohorts investigating alternative doses of selumetinib and vandetanib in combination.

The dosing regimen for each new cohort will be communicated and confirmed to clinical sites following the dose review meetings on completion of each cohort.

Cycle 1 will consist of 42 days. This includes the 14 days of vandetanib alone plus the 28 days of combination treatment.

Subsequent cycles will be of 28 days in length and consist of continuous treatment with vandetanib and selumetinib at steady state. There is no planned interval between cycles. Patients may continue to receive the combination therapy in the absence of disease progression or unacceptable toxicity (please see Section 5.6).

Pharmacokinetic parameters will also be measured pre and post treatment with single agent vandetanib and following combination treatment with selumetinib.

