5.4.2.1 Vandetanib and Selumetinib dose reduction

During single agent (vandetanib) phase

If vandetanib administration is interrupted during the single agent phase at the start of Cycle 1 (first 14 days):

- If the interruption was unrelated to vandetanib, administration can recommence as per protocol with no dose reduction.
- If the interruption was related to vandetanib,
 - If toxicity \leq G2, administration can continue as per protocol with no dose reduction on return to Grade 1 or baseline.
 - If toxicity is Grade 3 or above the patient must permanently discontinue study treatment.

During combination phase

If combination treatment is interrupted for **<10 days** during the combination treatment, on re-starting treatment:

- If the interruption was **unrelated to vandetanib or selumetinib**, both drugs can be administered together in combination following the interruption with no dose reduction.
- If the interruption was **related to vandetanib**, on return to Grade 1 or below, vandetanib should be dose reduced to the next lowest dose level od*. A dose reduction to selumetinib is not mandated.

*If single agent dose is 100mg then administration of vandetanib given every other day can be considered however selumetinib must also be administered in combination (selumetinib is not to be administered as a single agent).

- If the interruption was related to selumetinib, on return to Grade 1 or below, selumetinib should be dose reduced to next lowest dose level. A dose reduction to vandetanib is not mandated.

If combination treatment is interrupted for 10-14 days, on re-starting treatment:

- If the interruption was unrelated to vandetanib or selumetinib, vandetanib should be administered as a single agent (no dose reduction) for 10 days at steady state dose level (dependant on cohort) before re-introducing selumetinib (no dose reduction).
- If the interruption was related to vandetanib, vandetanib should be administered as a single agent for 10 days at the next lowest dose level od* before re-introducing selumetinib. A dose reduction to selumetinib is not mandated.
*If single agent dose is 100mg then administration of vandetanib given every other day can be considered however following re-loading, selumetinib must also be administered in combination with vandetanib every other day (selumetinib is not to be administered as a single agent).

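### For a vandetanib-related DLT in Cohorts 2 and 3, Section 5.4.2 lowers selumetinib while Section 5.4.2.1 lowers vandetanib, and the protocol states no order of precedence

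*Protocol*

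**What the plan says.** Section 5.4.2 opens with its scope: "This section is applicable to both the dose escalation phase and also the expansion cohort". It then gives a rule that does not depend on which drug caused the event: "The dose of the combination treatment will be reduced to the previous dose level for any patient who experiences a DLT". It also bars later re-escalation.

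Section 5.4.2.1, a subsection of 5.4.2, works by attribution. For a vandetanib-related interruption of less than 10 days in the combination phase, "vandetanib should be dose reduced to the next lowest dose level od*. A dose reduction to selumetinib is not mandated". For a selumetinib-related one, "selumetinib should be dose reduced to next lowest dose level. A dose reduction to vandetanib is not mandated". A footnote covers patients already on the lowest vandetanib dose: "If single agent dose is 100mg then administration of vandetanib given every other day can be considered". In the 10-14 day path the same footnote continues that "selumetinib must also be administered in combination with vandetanib every other day (selumetinib is not to be administered as a single agent"). The footnote for shorter interruptions requires selumetinib to be given in combination but does not state the day pattern.

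The table in Section 5.4.2.2 gives two choices for a first selumetinib reduction: the original dose once daily, or one level lower twice daily.

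The dose levels are in Section 3.2.1: "The first three cohorts will initially investigate combining vandetanib (100mg, once daily) with increasing doses of selumetinib". Those selumetinib doses are 25, 50 and 75 mg bd.

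Section 3.1.1 lists QTc above 500 msec as a DLT. Appendix 16.6 withholds treatment above 480 ms. On resumption it reduces vandetanib, by alternate-day dosing at the same level, and mentions no move to the previous combination level.

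**The concern.** A patient with a DLT will usually fall under both sections. Under Section 3.1.1 a DLT is at least probably related to one of the drugs, and Section 5.4.1 generally requires drug-related toxicity to lead to withholding, with listed exceptions such as skin toxicity and nausea. The interruption then brings in 5.4.2.1, while the DLT itself brings in 5.4.2. For a vandetanib-related event in Cohorts 2 and 3 the two sections change different drugs, and nothing says which governs.

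The patients concerned are those with the most severe toxicity. The regimen on which they resume supplies later-cycle safety data, which Section 3.1.1 says will be considered in determining the RP2D, and the dose-modification data described under Section 13.1. If sites follow different sentences, those data come from different regimens for the same event.

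**Working it through.** No power or sample-size figure is involved. The check applies each rule as written to the Section 3.2.1 dose table.

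**Starting daily doses (vandetanib / selumetinib)**
- Cohort 1: 100 mg / 2 × 25 = 50 mg
- Cohort 2: 100 mg / 2 × 50 = 100 mg
- Cohort 3: 100 mg / 2 × 75 = 150 mg

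**Vandetanib-related DLT**

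| Cohort | Section 5.4.2 alone | Section 5.4.2.1, alternate-day option used |
|---|---|---|
| 3 | vandetanib 100 mg (0%); selumetinib 150 to 100 mg/day: (100 − 150)/150 = −33% | vandetanib averages 100/2 = 50 mg/day (−50%); no required change of selumetinib level |
| 2 | vandetanib 100 mg (0%); selumetinib 100 to 50 mg/day: (50 − 100)/100 = −50% | vandetanib averages 50 mg/day (−50%); no required change of selumetinib level |
| 1 | no previous level, so cannot be applied as worded | vandetanib averages 50 mg/day (−50%); no required change of selumetinib level |

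The alternate-day option is permissive, so the 50% applies only where it is used.

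**Selumetinib day pattern.** If selumetinib is given only on vandetanib days, its average also halves: in Cohort 3, 150/2 = 75 mg/day, with the level itself unchanged. The 10-14 day footnote states this pattern. The shorter-interruption footnote leaves it to be inferred from the ban on single-agent selumetinib.

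**QTc example.** A QTc above 500 msec also exceeds the 480 ms action threshold of Appendix 16.6. (Section 3.1.1 names no correction formula; the appendix uses Bazett, and this assumes the same one.) The appendix resumes vandetanib on alternate days. In Cohorts 2 and 3 the Section 5.4.2 sentence by itself leaves vandetanib at 100 mg od and lowers selumetinib.

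**Selumetinib-related DLT.** Sections 5.4.2 and 5.4.2.1 agree in Cohorts 2 and 3: selumetinib down one level, vandetanib unchanged. The 5.4.2.2 table adds the once-daily choice.
- Cohort 3: 75 mg od is 75 mg/day, (75 − 150)/150 = −50%, against −33% for 50 mg bd.
- Cohort 2: 50 mg od and 25 mg bd both total 50 mg/day, so only the schedule differs.
- Cohort 1: 25 mg od is 25 mg/day (−50%), and is the only one of the two choices that exists.

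**The case against.** The best defence is that the sections can be read together. Section 5.4.2.1 makes a selumetinib reduction optional and does not forbid it, so a site could reduce both drugs and satisfy both sentences. Section 5.4.2 is the parent heading, and reading it as the general rule with its subsections as detail is natural. On that reading the drug held responsible is not left unreduced. This stands in part: the two sections do not exclude each other. But a selumetinib reduction remains mandatory under one sentence and optional under the other, so a site that correctly follows 5.4.2.1 alone departs from 5.4.2.

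A second defence assigns 5.4.2 to DLTs and 5.4.2.1 to all other interruptions. The text does not say so, and 5.4.2.1 sits inside 5.4.2.

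It is also fair that escalation decisions and the MTD rest on first-cycle DLTs, which are counted before any reduction takes place. The effect on the RP2D is indirect.

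Several stronger readings might be inferred, and the documents do not support them:
- **Opposing reductions in all three cohorts.** Cohort 1 has no previous level, so the problem there is a sentence that cannot be applied.
- **No reduction rule at all in Cohort 1.** Section 5.4.2.2 offers once-daily selumetinib and requires discontinuation when toxicity that needs interruption recurs on the lowest schedule.
- **Daily selumetinib with alternate-day vandetanib after a short interruption.** This is strained, because the ban on single-agent selumetinib is in that same footnote and is repeated elsewhere.
- **A clash over the DLT defined by an interruption of more than 14 days.** Section 5.4.1 says "Patients failing to recover to NCI CTCAE Grade 1 or less after two weeks will be withdrawn from the study". A withdrawn patient has no dose left to reduce, and Section 5.4.2 does not say that every patient with a DLT continues. Death is also a listed DLT, so the sentence can only concern patients who resume.

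**Conclusion.** The conflict is real in a bounded form. For a vandetanib-related DLT in Cohorts 2 and 3, Section 5.4.2 requires less selumetinib and by itself leaves vandetanib unchanged. Section 5.4.2.1, and Appendix 16.6 for QTc, reduce vandetanib without requiring a selumetinib reduction. In Cohort 3 the contrast is selumetinib down 33% with vandetanib unchanged, against vandetanib down 50% if alternate-day dosing is chosen.

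Three lesser gaps go with it: the additional once-daily choice in 5.4.2.2 for selumetinib-related DLTs, the missing previous level in Cohort 1, and the unequal footnotes.

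This rests on the Cohort 1 to 3 doses and on the DLT also causing an interruption. For later cohorts the sponsor confirms the doses. For the expansion cohort the RP2D is not fixed in the document. The size cannot be worked out for either, although Section 5.4.2 applies to both phases.

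**What to change.** The sponsor and investigators should reconcile the Section 5.4.2 sentence with Sections 5.4.2.1 and 5.4.2.2 and Appendix 16.6, so that one stated rule governs reduction after a DLT. The text should say:
- which passage takes precedence, and whether attribution decides which drug changes;
- how the rule applies in Cohort 1;
- whether the once-daily selumetinib choice is available after a DLT;
- the selumetinib day pattern, in the same words in both footnotes of 5.4.2.1.

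The content of the rule is a clinical decision for them, and no dose or rule is proposed here. The cost is amendment wording and a short instruction to sites, with no added visits or patients.

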5.4.2.1 Vandetanib and Selumetinib dose reduction

During single agent (vandetanib) phase

If vandetanib administration is interrupted during the single agent phase at the start of Cycle 1 (first 14 days):

- If the interruption was unrelated to vandetanib, administration can recommence as per protocol with no dose reduction.
- If the interruption was related to vandetanib,
 - If toxicity \leq G2, administration can continue as per protocol with no dose reduction on return to Grade 1 or baseline.
 - If toxicity is Grade 3 or above the patient must permanently discontinue study treatment.

During combination phase

If combination treatment is interrupted for **<10 days** during the combination treatment, on re-starting treatment:

- If the interruption was **unrelated to vandetanib or selumetinib**, both drugs can be administered together in combination following the interruption with no dose reduction.
- If the interruption was **related to vandetanib**, on return to Grade 1 or below, vandetanib should be dose reduced to the next lowest dose level od*. A dose reduction to selumetinib is not mandated.

*If single agent dose is 100mg then administration of vandetanib given every other day can be considered however selumetinib must also be administered in combination (selumetinib is not to be administered as a single agent).

- If the interruption was related to selumetinib, on return to Grade 1 or below, selumetinib should be dose reduced to next lowest dose level. A dose reduction to vandetanib is not mandated.

If combination treatment is interrupted for 10-14 days, on re-starting treatment:

- If the interruption was unrelated to vandetanib or selumetinib, vandetanib should be administered as a single agent (no dose reduction) for 10 days at steady state dose level (dependant on cohort) before re-introducing selumetinib (no dose reduction).
- If the interruption was related to vandetanib, vandetanib should be administered as a single agent for 10 days at the next lowest dose level od* before re-introducing selumetinib. A dose reduction to selumetinib is not mandated.
*If single agent dose is 100mg then administration of vandetanib given every other day can be considered however following re-loading, selumetinib must also be administered in combination with vandetanib every other day (selumetinib is not to be administered as a single agent).
- If the interruption was related to selumetinib, vandetanib should be administered as a single agent for 10 days at the same dose level od (no dose reduction) before re-introducing selumetinib at the next lowest dose level.

Administration of vandetanib given every other day can be considered following a dose interruption however selumetinib must also be administered in combination.

Selumetinib must not be administered as a single agent.

5.4.2.2 Selumetinib dose reduction

Modification	Selumetinib original dose (at time of dose modification)	Selumetinib reduced dose
1	Original dose (twice daily)	Original dose (once daily) or Reduce by one dose level (twice daily)
2	Original dose (once daily)	Reduce by one dose level (twice daily)
3	Reduced dose level (twice daily)	Reduced dose level (once daily)

Following a dose reduction, the dose will not be escalated again for that patient.

a) Following an initial dose reduction, if a patient experiences an occurrence of a new toxicity requiring treatment interruption, selumetinib should again be withheld until the toxicity improves to CTCAE (version 4.02) Grade 1 or baseline, except for rash where CTCAE Grade 2 rash is acceptable. Upon recovery, treatment may resume as follows:

- The current dose can be reduced to either a once daily administration or
- The dose administered can be at the previous dose level (as investigated in the dose escalation phase) and be administered twice daily (if dose reduction to once daily administration has already taken place).

b) If a patient experiences a recurrence of the same toxicity as that causing a previous dose interruption and/or dose reduction, selumetinib should be withheld until the toxicity improves to CTCAE (version 4.02) Grade 1 or baseline, except for rash where CTCAE Grade 2 rash is acceptable. Upon recovery, treatment should resume at a permanently reduced or adjusted dose:

- 1) Once daily: if no dose reduction has yet occurred
- 2) Reduced dose, twice daily: (if dose reduction to once daily has already occurred)
- 3) Reduced dose, once daily: if steps (1) and (2) have already occurred.

If a patient experiences recurrence of any toxicity requiring dose interruption whilst receiving the lowest dosing schedule for this study, the patient must discontinue study treatment.

If a patient receiving the lowest dosing schedule experiences a novel toxicity that cannot be adequately managed by dose interruption and medical interventions then the patient must discontinue study treatment, as no further dose reductions/adjustments are permitted.

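### In 5.4.2.2, a patient cut from 75 mg bd to 75 mg od moves after further toxicity to 50 mg bd, so daily selumetinib rises from 75 to 100 mg

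*Protocol*

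**What the plan says.** The table in Protocol 5.4.2.2 has three modifications. Row 1 takes a patient on the original dose twice daily to "Original dose (once daily) or Reduce by one dose level (twice daily". Row 2 takes a patient on the original dose once daily to one level lower, twice daily. Row 3 takes that lower level from twice to once daily.

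Two lists repeat the order. List (a), for a new toxicity after an initial reduction, is permissive. Its second bullet allows the previous level to "be administered twice daily (if dose reduction to once daily administration has already taken place". List (b), for recurrence of the same toxicity, says treatment should resume in sequence: first "Once daily: if no dose reduction has yet occurred", then "Reduced dose, twice daily: (if dose reduction to once daily has already occurred", then the reduced dose once daily.

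The same section states: "Following a dose reduction, the dose will not be escalated again for that patient". Section 5.4.2 says: "If a patient has a dose reduction, their dose should not be re-escalated". Section 5.3.1 also rules out escalation within a patient. These reduction rules apply to both the escalation phase and the expansion cohort.

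**The concern.** A reduction ladder should lower exposure at each step. Here, one route restarts a patient after a further toxicity on more drug per day than when that toxicity occurred, while the section says the dose will not go back up. This is a first-in-human combination whose toxicities the protocol expects to overlap. A site following the table would raise daily exposure and believe it had reduced it.

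Row 2 has a second gap. Sections 1.4.2 and 5.3 allow once-daily selumetinib cohorts. Read literally, row 2 moves a patient assigned to once-daily dosing to the next lower level twice daily, which can raise the daily total at that patient's first reduction.

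**Working it through.** **Inputs.** The dose levels are 25, 50 and 75 mg bd (3.2.1). The half-life is 5 to 7 h, tmax is 1.5 h and pharmacokinetics are approximately dose proportional (2.2.2.3). The protocol states no mg/day for the ladder, so there is no figure of its own to reproduce.

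**Daily total** = mg per administration × administrations per day.

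| Start and route | Steps | mg/day |
|---|---|---|
| 75 mg bd, once-daily route | 75 bd, 75 od, 50 bd, 50 od | 150, 75, **100**, 50 |
| 75 mg bd, lower-level route | 75 bd, 50 bd, 50 od | 150, 100, 50 |
| 50 mg bd, once-daily route | 50 bd, 50 od, 25 bd, 25 od | 100, 50, **50**, 25 |
| 50 mg bd, lower-level route | 50 bd, 25 bd, 25 od | 100, 50, 25 |
| 25 mg bd | 25 bd, 25 od; no lower level named | 50, 25 |

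The marked step from 75 mg bd is 100/75 − 1 = +33%. From 50 mg bd it is 50/50 − 1 = 0%. With dose-proportional pharmacokinetics, 24-hour exposure changes in the same proportion.

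**Once-daily cohorts.** For an assigned dose D od and next lower level L, row 2 gives 2L mg/day. This is a rise whenever L > D/2. The protocol fixes no once-daily level. If 75 mg od were assigned with 50 mg as the next level, the move would be 75 to 100 mg/day.

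**Steady-state peak.** Assume one compartment, linear kinetics and instant absorption. Peak = D/(1 − exp(−kτ)), with k = ln 2/half-life, in mg-equivalents.

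- Half-life 5 h: 75 od gives 75/(1 − 0.0359) = 77.8; 50 bd gives 50/(1 − 0.1895) = 61.7; change −20.7%.
- Half-life 7 h: 75 od gives 75/(1 − 0.0929) = 82.7; 50 bd gives 50/(1 − 0.3048) = 71.9; change −13.0%.

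Now assume first-order absorption, with ka solved from ln(ka/k)/(ka − k) = 1.5 h. The peak is the maximum over one interval of D·ka/(ka − k) × [exp(−kt)/(1 − exp(−kτ)) − exp(−ka·t)/(1 − exp(−ka·τ))].

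- Half-life 5 h: 63.4 to 51.0, change −19.6%.
- Half-life 7 h: 71.6 to 63.1, change −11.9%.

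**Steady-state trough**, instant absorption (peak × exp(−kτ)): 2.8 to 11.7 at 5 h and 7.7 to 21.9 at 7 h, a rise of about 4.2- and 2.9-fold.

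So on this step the total and the trough rise while the peak falls.

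**The case against.** The best defence is that dose means mg per administration. The table uses one label for the original dose at either frequency, and list (a) names the level and the frequency separately. On that reading 75 to 50 mg is a reduction and nothing is broken. List (b) also speaks of a reduced or adjusted dose, which leaves room for steps that are not plain reductions. This lowers confidence but does not settle the matter. The section places the unchanged amount once daily in its reduced-dose column, and the wording of (b)(2) itself calls that change a dose reduction. If halving the frequency is a reduction, doubling it again cannot simply be ignored.

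The path is also narrow, and this stands in full. For DLTs, 5.4.2 says "The dose of the combination treatment will be reduced to the previous dose level for any patient who experiences a DLT". For selumetinib-related interruptions, 5.4.2.1 says "selumetinib should be dose reduced to next lowest dose level". Row 1 offers 50 mg bd directly, list (a) only permits the step, and Appendix 16.5 stops treatment when severe skin toxicity recurs at reduced doses. Only (b)(2) directs the step, after an entry that is optional or uncommon.

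A reader might infer that patients are put at greater risk. The documents do not support that. They do not say whether total exposure or peak drives toxicity. Under the escalation rules, 50 mg bd is reviewed for DLTs before 75 mg bd opens. Section 2.3.5 reports that 50 mg bd was not tolerated with erlotinib and recommends 100 mg od. That involves a different partner drug and equal daily totals (100 mg), so it shows only that a lower peak cannot be assumed to be better tolerated.

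**Conclusion.** As written, the once-daily route from 75 mg bd raises the daily total by one third after further toxicity, and from 50 mg bd it leaves the total unchanged. The arithmetic is certain. The contradiction with the no-escalation rule is held with moderate confidence, because it rests on the section's own use of reduction for a change of frequency.

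The importance lies between minor and should-fix. On a 75 mg bd start the patient stays below 150 mg/day, the probable peak falls by 12 to 21% under the stated assumptions, and net harm is not shown. A reader might also infer that the whole ladder is faulty. It is not: the lower-level route falls at every step. The protocol gives no basis for counting the patients affected.

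**What to change.** Keep the once-daily first step. Change row 2, the second bullet of (a), and (b)(2) to one dose level lower, once daily. The once-daily route then runs 150, 75, 50 mg/day from 75 mg bd and 100, 50, 25 mg/day from 50 mg bd.

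Limit row 3 and (b)(3) to patients whose first reduction was one level lower twice daily (150, 100, 50 mg/day from 75 mg bd). Replace the present condition in (b)(3), which requires steps 1 and 2 to have occurred. Any patient already at the lower level twice daily by the existing route needs row 3 kept open.

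Also state that:
- a 25 mg bd start has only 25 mg od, then discontinuation;
- patients assigned to once-daily dosing reduce to the next lower level once daily;
- no step may raise total mg/day, with mg/day shown in the table for each starting level.

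The cost is amendment wording in one table and two lists, with no added patients or assessments. The downside is that patients on the once-daily route receive 50 instead of 100 mg/day at the second step from 75 mg bd, and have one fewer reduction before discontinuation. Removing the once-daily first step would also make the ladder fall throughout, but it would give up the 50% first cut and send 75 mg bd patients to 100 mg/day after their first toxicity.
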